6.1 Data Monitoring

An external, independent Data Safety Monitoring Board (DSMB) will be established to provide a review of study safety while the study is ongoing. The composition and membership is being confirmed and we hope to include: a paramedic researcher, an emergency physician, a nurse familiar with the application of the CCR, a paramedic representative, a statistician and a pediatric emergency physician.

We have developed Terms of Reference for the DSMB, using the guidance provided by OHRI, entitled *Data and Safety Monitoring Guidelines for Clinical Trials*, as well as the Terms of Reference used for our previous single-centre evaluation of the CCR. The Terms of Reference will be reviewed by the Study Steering Committee, before being sent for review and approval to the OHRI's Research Administrative Committee. The most up-to-date version of the Terms of Reference has been appended to the study protocol (see Appendix 8. Data Safety Monitoring Board Terms of Reference).

All members of the DSMB will be required to complete and sign a Confidentiality Agreement, which will be kept on file by the study team. The DSMB members will familiarize themselves with the Study Protocol, as well as the Terms of Reference. The content and information available for review will depend on the availability of outcomes provided by ICES. At a minimum, the DSMB members will be provided with a report including information on accrual, application of the CCR by paramedics, protocol deviations, mechanism of injury and other data points collected from the paramedic documentation. If available for interim analyses, information provided by ICES on imaging and c-spine injuries will be included in the report for review. Due to the short intervention, this information may only be available in a final report.

The meeting frequency has not yet been finalized, but we anticipate the DSMB will meet very shortly after data collection begins, followed by another meeting approximately six months later. The DSMB may also meet to review the final report. Following each meeting, the DSMB will complete a report to be submitted to the Principal Investigator. The report will be presented to the Steering Committee and will also be sent to the REB, as well as OHRI's Research Administration Committee. We will respond to any concerns raised by the DSMB and provide additional information requested. Any corresponding changes to the protocol will be documented in Table 2.

6.2 Data Monitoring - Interim Analyses

The intervention period for this multi-centre study is fairly short - only 12 months long. Because of this, there are no interim analyses planned.

The number of c-spine injuries in eligible patients will be monitored as outcome information is available. We plan to obtain preliminary information on a small subset of study outcomes for safety assurance purposes before the first cluster of centres begin actively using the CCR. We will send the required information to ICES based on the first two months of enrollment following training (see Figure 2). Analysts at ICES will link our data at that time with the information available from the Ontario Health Insurance Plan (OHIP) database, as well as the Canadian Institute for Health — Discharge Abstract Database (CIHI-DAD). This will give us information on which cases had c-spine imaging performed, and of those, whether any c-spine injuries were identified. We will then review these cases to ensure that the CCR was applied appropriately and that no injuries were missed by either the paramedics, or the CCR itself.

The only situation that would trigger an immediate review to consider stopping the trial would be a situation where a spinal cord injury was sustained by an enrolled patient and believed to be a direct consequence of having transported a patient without immobilization resulting from the use of the CCR. In this case, we would notify the DSMB to review the available information and discuss their review and recommendations with the Steering Committee.

We would not consider a missed significant injury sufficient to warrant stopping the study as long as there was no consequence to the patient's safety and health i.e. not resulting in a spinal cord injury that was not already present before transport to the hospital. Any missed significant injury will be reported to both the DSMB and Research Ethics Board in a timely manner.

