6.3 Harms

Adverse events will be classified according to the following definitions:

- 1. Protocol Deviations this category will include cases where the CCR was applied to the wrong patient population, or situations where the rule was applied inaccurately in the opinion of study staff. These will be included in DSMB reports for review at scheduled meetings.
- Adverse Events This category will include transport of patients without immobilization later determined to have an important cervical spine injury. This may include cases where the rule was applied incorrectly by the treating paramedic, or cases missed by the CCR. These cases will be reported to the DSMB and the REB for review and consideration.
- 3. Serious Adverse Events – This will include patients transported without immobilization who are later determined to have suffered a spinal cord injury with neurological deficit. If such a case was to ever occur, the study would immediately be stopped pending DSMB and REB ruling on whether the study can resume or not. Note: such a serious adverse event has never been observed in more than 36,000 patients evaluated with the CCR in various research studies this far.

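### Section 6.2 and Section 6.3 (with DSMB Appendix B) set different triggers for the trial's one pre-stated harm-stopping event

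*Combined protocol and SAP*

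**What the plan says.** Section 6.2 plans no interim analyses and names a single event for urgent action. "The only situation that would trigger an immediate review to consider stopping the trial" is a spinal cord injury in an enrolled patient that is "believed to be a direct consequence of having transported a patient without immobilization" as a result of using the CCR. The action is to notify the DSMB, which reviews the case and discusses its recommendations with the Steering Committee.

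The next paragraph of Section 6.2 says "We would not consider a missed significant injury sufficient to warrant stopping the study", provided the patient's safety and health did not suffer. It explains that proviso as "not resulting in a spinal cord injury that was not already present before transport to the hospital". It adds: "Any missed significant injury will be reported to both the DSMB and Research Ethics Board in a timely manner".

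Section 6.3 defines a serious adverse event as "patients transported without immobilization who are later determined to have suffered a spinal cord injury with neurological deficit". If one occurs, "the study would immediately be stopped pending DSMB and REB ruling on whether the study can resume or not". Appendix B of the DSMB Terms of Reference (protocol Appendix 8) uses the same definition and the same action, under the label of severe adverse events.

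**The concern.** A stopping rule for harm should give one answer for one patient. Here the first text makes causality and timing conditions for acting, while the other two act first and have no such conditions. If a cord injury with deficit came to light in a non-immobilized patient and someone judged it to predate transport, the investigators would hold one text that says stopping is not warranted and two that stop the study immediately.

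Section 6.2 also does not say who makes that judgement, although under its wording the judgement decides whether an immediate review is triggered at all. What is at stake is whether paramedics go on using the CCR until the DSMB and REB have ruled. The matter deserves clear drafting because this is the only harm event for which the protocol prescribes a stop or an urgent review in advance, and because the trial seeks a waiver of consent (Section 7.3).

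**Working it through.** No arithmetic applies. The check sets the texts side by side for a patient transported without immobilization.

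**Conditions for acting**

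| | Section 6.2 | Section 6.3 and Appendix B |
|---|---|---|
| Cord injury needed | Yes | Yes |
| Neurological deficit needed | Not stated | Yes |
| Causal link to transport needed | Yes | No |
| Must be new since transport | Yes, by the explanatory clause | No |
| Action | DSMB review, discussion with Steering Committee | Immediate stop until DSMB and REB rule |

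**Outcome by case**

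1. *Cord injury with deficit, believed caused by the transport.* Section 6.2 gives immediate review; the other two give an immediate stop. These are compatible, although Section 6.2 mentions neither a halt nor an REB ruling.
2. *Cord injury with deficit, judged already present before transport.* Section 6.2's trigger is not met, and its explanatory clause places the case among missed injuries that do not warrant stopping; it is reported to the DSMB and REB. Section 6.3 and Appendix B stop the study. The instructions differ.
3. *New deficit, judged not caused by the transport.* It lies outside Section 6.2's single trigger. Section 6.2 does not name this case, so the absence of an immediate review is an inference. Section 6.3 and Appendix B stop the study. The instructions differ.
4. *Cord injury without deficit, believed caused by the transport.* It reaches the DSMB under Section 6.2 and, as an important cervical spine injury, through the adverse-event class of Section 6.3. It is not part of this point.

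**Can the texts be reconciled?**

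- *Stopping in Section 6.2 means final termination, and stopped in Section 6.3 means a pause.* This fails because Section 6.2 restricts even an immediate review to its one causal situation, whereas Section 6.3 halts the study on a trigger without that restriction.
- *Suffered in Section 6.3 means suffered during transport.* The definition turns on what is later determined and sets no time of onset. Appendix B repeats it without one. Section 6.2 shows that the authors wrote timing and causal conditions where they wanted them.
- *An order of precedence.* None of the three texts gives one.

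**How often could cases 2 and 3 arise?** Acute paralysis is an exclusion (Section 3.2 and Appendix 6), and numbness or tingling in the extremities mandates immobilization under the CCR (Appendix 6). For case 2, that leaves mainly partial or unrecognised deficits and misapplied rules. Section 6.3 also notes that "such a serious adverse event has never been observed in more than 36,000 patients evaluated with the CCR". The probability of the conflicting cases cannot be estimated from the documents.

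**The case against.** The strongest defence is that the sections run largely in parallel. Section 6.2's cord-injury sentence matches the serious tier of Section 6.3, and its missed-injury sentence matches the adverse-event tier, with reporting to the DSMB and REB in both. The words that create the conflict for a pre-existing deficit sit at the end of a double negative in an explanatory clause, and that clause does not mention deficit. One could halt first under Section 6.3 and then resume under Section 6.2 once the injury is judged pre-existing. In part this stands: the no-stop instruction is read from that clause rather than stated as a rule of its own. It does not remove the mismatch, because Section 6.2 excludes an immediate review in any other situation.

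The practical objection is also fair. Injury data from the administrative linkage may arrive only with the final report (Section 6.1), when nothing remains to be stopped, and the planned early linkage covers enrolment before any service uses the CCR (Section 6.2). The conflict therefore bites only for injuries that come to light during the CCR phase.

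Three stronger readings are tempting and not supported:

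- *Safety oversight fails.* It does not. Section 6.2 reports every missed significant injury, and under its Terms of Reference the DSMB meets on unexpected adverse events (2.0) and may recommend early termination for patient safety (5.0). These powers are discretionary, so they leave open only what happens before the DSMB rules.
- *The size can be shown by counting patients seen during a halt.* Any such count would apply to a pause for any reason, with no stated length, and does not measure the wording problem.
- *The results are biased or power is lost.* Nothing in the wording conflict touches the effect estimate or the power calculation.

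**Conclusion.** The point holds as a minor drafting inconsistency in a safety rule. For a deficit judged pre-existing, Section 6.2 and Section 6.3 with Appendix B cannot both be followed; for a new deficit judged non-causal, the same conclusion rests on inference. The consequence is confined to conduct and oversight, in a case that should be rare.

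The conclusion assumes that the explanatory clause in Section 6.2 means what it literally says about injuries present before transport, and that the definition in Section 6.3 carries no unstated causal or timing limit. If the sponsor intended such a limit, the documents do not say so.

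**What to change.** Before the first services cross to the CCR, amend Section 6.2 only. Replace its trigger with the rule already in Section 6.3 and Appendix B: any cord injury with neurological deficit in a patient transported without immobilization stops the study immediately until the DSMB and REB have ruled. State that causality and pre-existence are considered in that ruling and are not preconditions for the stop. Make the missed-injury sentence subject to this rule, so that its clause on injuries present before transport no longer points the other way. Leave Section 6.3 and Appendix B unchanged. A cord injury without deficit would still go to the DSMB and REB through the adverse-event class of Section 6.3; the sponsor can keep the existing review sentence for that case if it wishes.

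Adding a causal condition to Section 6.3 and Appendix B would also remove the mismatch, but it would change two texts and loosen the stricter rule.

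The cost is one protocol amendment through the Steering Committee and the REB (Section 7.2), including any REB outside the Clinical Trials Ontario arrangement. The downside is a possible short halt for an injury later judged unrelated, which Section 6.3 and Appendix B already accept.

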6.3 Harms

Adverse events will be classified according to the following definitions:

- 1. Protocol Deviations this category will include cases where the CCR was applied to the wrong patient population, or situations where the rule was applied inaccurately in the opinion of study staff. These will be included in DSMB reports for review at scheduled meetings.
- Adverse Events This category will include transport of patients without immobilization later determined to have an important cervical spine injury. This may include cases where the rule was applied incorrectly by the treating paramedic, or cases missed by the CCR. These cases will be reported to the DSMB and the REB for review and consideration.
- 3. Serious Adverse Events – This will include patients transported without immobilization who are later determined to have suffered a spinal cord injury with neurological deficit. If such a case was to ever occur, the study would immediately be stopped pending DSMB and REB ruling on whether the study can resume or not. Note: such a serious adverse event has never been observed in more than 36,000 patients evaluated with the CCR in various research studies this far.

6.4 Auditing

We plan to conduct regular site visits with all participating sites. The initial visit will be primarily to go over training material with local study staff, go over study requirements, and ensure local study staff have all the necessary study documentation. The intervention is twelve months in length. We will conduct one subsequent visit to each site during the invention phase to ensure that study documentation is accurate and up to date, and that all study material is accurate and up to date and that local study procedures are being conducted as per the study protocol. If concerns are noted, we will work individually with each site to address the concern and rectify the situation.

Section 7. Ethics and Dissemination

7.1 Research Ethics Approval

The study protocol and all study-related documents (EMS CCR, study data collection) will be submitted to the Ottawa Health Sciences Network Research Ethics Board (OHSN-REB) for review and approval. The OHSN REB has recently become a board of record for Clinical Trials Ontario. As a result, and because this is a multi-centre study, the study protocol will be submitted to the OHSN-REB through Clinical Trials Ontario. All participating sites that have existing agreements in place with Clinical Trials Ontario will be included in the initial REB Submission. We will identify a local site investigator and help coordinate REB submission, review and approval for those sites that do not have agreements with Clinical Trials Ontario.

7.2 Protocol Amendments

Any changes to the protocol including to the study objectives, design, patient population, sample size, or procedures will be first reviewed and approved by the Steering Committee and noted in this document. The amended protocol will then be sent through Clinical Trials Ontario to the OHSN-REB. Once approved, all sites included on the Clinical Trials Ontario application will receive notification of the amendment. We will submit amendments to the additional REBs who are not part of Clinical Trials Ontario.

7.3 Consent

We will be seeking a waiver of informed consent from the OHSN-REB. This was the case in the previous multi-centre prehospital validation of the CCR, as well as the single-centre prehospital implementation study. The study protocol has been reviewed by the Medical Advisory Committee for the Ontario Base

Hospitals Group (MAC – OBHG). The MAC provides advice to the Emergency Health Services Branch (EHSB) of the Ontario Ministry of Health and Long-Term Care. Paramedics employed by EMS Services participating in the study will be allowed via a Medical Directive to use the CCR to evaluate eligible patients instead of the usual immobilization protocols. The Medical Directive will be drafted by the MAC-OBHG and authorized by the EHSB for the duration of the study.

7.4 Confidentiality

Paramedics will evaluate eligible patients using the CCR. They will complete an electronic form that will capture information on the elements of the CCR, as well as pain, patient comfort, and paramedic comfort with using the CCR. The electronic form will not include any information that can identify a patient. Upon receipt of the electronic form, study staff will assign a unique study number. We will also receive the corresponding paramedic documentation electronically that will allow us to capture the remainder of the pre-hospital data required. The paramedic documentation will also be transmitted electronically, stripped of patient identifiers.

In order to link the pre-hospital information with the data housed at ICES, we will need to maintain a list of eligible enrolled patients, including first name, last name, date of birth, sex, postal code, health card number (where available). This list will be generated and maintained by staff at each Base Hospital, or EMS Service if Base Hospital staff are unable to access this information. The information will be stored in a password-protected, encrypted spreadsheet. When this information is required by ICES for linkage purposes, it will be transmitted securely according to their protocols. The linked information that we receive back from ICES will be stripped of personal identifiers before we receive it. All paper study files will be stored in locked filing cabinets in a locked office. All electronic files will be stored on limited-access network folders which are backed up regularly. Any information shared with DSMB Members or other study committees will not include any identifiable information.

7.5 Declaration of Interests

All study members with affiliations to the Ottawa Hospital Research Institute are required to disclose information on competing interests at least once per year. We will require study members to report annually on any real or potential conflicts of interest. This information will be compiled and made available to the entire study team.

7.6 Access to Data

All personal health information will be kept confidential, unless release is required by law. Representatives of government regulators such as Health Canada, representatives of the Ottawa Health Sciences Network Research Ethics Board, as well as the Ottawa Hospital Research Institute, may review the records under the supervision of [name] staff for audit purposes.

Any study information that is shared with participating sites will not have any identifying information. Each study subject will be assigned an independent study number. The link between patient name and independent study number will only be accessible by [name] and/or his staff and will be stored separately and securely from the study files.

- Minutes will be kept for all meetings and circulated to the membership within two weeks of each meeting. Once approved, they will be posted to a restricted-access location on the study website.
- Communications between C-Spine PC members will be largely via email or telephone. All official
 email related to C-Spine PC business will be copied to the Chair and Study Coordinator ([name])
- A webpage detailing the activities and responsibilities of the C-Spine PC will be incorporated into
 the main study website, where guidance material, meeting minutes and other resources will
 also be found.

Version 3 - April 2016

Appendix 5. Patient Committee Terms of Reference To be appended once developed and finalized.

Appendix 6. Paramedic Data Collection Form

EVALUATION OF THE SAFETY OF C-SPINE CLEARANCE BY PARAMEDICS CALL NUMBER: DATE OF CALL (YY/MM/DD): 1. INCLUSION CRITERIA (check as applicable) ALERT (GCS 15) STABLE (SBP ≥90mmHg, respiratory rate 10-24/minute) **ACUTE BLUNT INJURY (<48 hours)** Are all the inclusion criteria met? ■ NO - STOP; can't use the Canadian C-Spine Rule 2. EXCLUSION CRITERIA (check as applicable) Boarded and collared for reason other than c-spine injury Age < 8 years Penetrating trauma from stabbing or gunshot wound Acute paralysis (paraplegia, quadriplegia) Known vertebral disease (ankylosing spondylitis, rheumatoid arthritis, spinal stenosis, previous c-spine surgery) Referred from another hospital Does the patient have any exclusion criteria? ☐ YES - STOP: can't use the Canadian C-Spine Rule ■ NO - CONTINUE 3. THE CANADIAN C-SPINE RULE START HERE 1. Any ONE high-risk factor which mandates immobilization? ☐ No ☐ Yes Age ≥65 years ☐ No ☐ Yes Dangerous Mechanism* ☐ No ☐ Yes Numbness or tingling in extremities ☐ YES - STOP ■ NO - CONTINUE 2. Any ONE **low-risk** factor which allows safe assessment of range of motion? ☐ No ☐ Yes Rearended in Simple Rearend MVC** ■ NO - STOP ☐ No ☐ Yes Ambulatory at any time at scene ☐ C-SPINE IMMOBILIZATION ☐ No ☐ Yes No neck pain at scene when asked (answer "yes" if no pain) ☐ No ☐ Yes No pain during midline c-spine palpation (answer "yes" if no pain) Dangerous Mechanism: -fall from elevation ≥3 feet/5 stairs □ NO ☐ YES - CONTINUE axial load to head, e.g. diving -MVC: rollover, ejection, high speed (≥100km/h) -motorized recreational vehicles, e.g. ATV, 3. Patient voluntarily able to actively rotate neck 45° left and right when snowmobile requested, regardless of pain? -bicycle collision with object, e.g. post, car ☐ No ☐ Yes **Simple Rearend MVC Excludes: -pushed into oncoming traffic ☐ YES -hit by bus/large truck -rollover ■ NO C-SPINE IMMOBILIZATION -hit by high speed vehicle (≥100km/h) 1. According to the Canadian C-Spine Rule, would this patient require immobilization? 2. How comfortable would you be in following the Canadian C-Spine Rule for this patient? very comfortable ☐ comfortable ☐ neutral □ uncomfortable very uncomfortable 3. If you were uncomfortable, please briefly describe why: 4. Will you use the Canadian C-Spine Rule when deciding whether or not to immobilize this patient? Yes, this patient will be transported with or without immobilization according to the Canadian C-Spine Rule. ☐ No, I am choosing to immobilize this patient, despite the rule indicating immobilization is not required. 5. Was there a language barrier present that hindered your ability to apply the Canadian C-Spine Rule to this patient? 🗖 No 🗖 Yes 6. Before transfer of care to the Emergency Department, please ask your patient the following questions: i) On a scale of 1 – 10 (10 being the highest level of pain), how would you rate your pain right now? ii) On a scale of 1-10 (10 being very uncomfortable), how would you rate your comfort level right now?
